8.1.5. Inverse Probability of Treatment Weighting (IPTW)

Weighting patients by the inverse probability of treatment received creates a synthetic sample in which treatment assignment is independent of measured baseline covariates. IPTW using the PS allows one to obtain unbiased estimates of average treatment effects. IPTW can be calculated based on the PS for each patient. The weight for the j th patient with PS P_j is:

$$W_j = 1 / P_j \text{ if in the treated group}$$

$$W_j = 1 / (1 - P_j) \text{ if in the control group}$$

Note: P_j is the probability of receiving the active treatment.

When using IPTW, a good practice is to normalize weights and make the sum of the total of weights within one cohort be 1. It can be achieved by dividing each patient's weight by the sum of all weights in that cohort. The nIPTW weight for patient j in a cohort with N patients can be calculated as:

$$W_j^* = W_j \times \frac{N}{\sum_{j=1}^N W_j}$$

After normalization, the total number of patients in the weighted population will stay the same as unweighted population.

8.1.6. Imputation of Missing Values for Baseline Covariates in Sensitivity Analyses

Missing values in baseline variables are not uncommon in real world data. Because the PS of a patient is the conditional probability of treatment given all observed covariates, missing data for any covariate can make the PS estimation more challenging. In primary

analysis, missing data are assigned to a new category of “Unknown” when PSs are estimated in multivariate logistic regression model.

To address the potential impact of missing values on PS estimation, and further on the estimation of the primary endpoint rwRR, the proportion and pattern of missing values will be evaluated, and sensitivity analyses may be performed using appropriate imputation methods (e.g. Multiple Imputation method [5]) to impute missing values for variables with missing data.

8.2. Statistical Analyses

The full analysis set is the primary population for estimating the PS, evaluating effectiveness and safety. All data analyses will be executed using statistical software SAS version 9.4 or later.

8.2.1. Estimate PS and Assess Feasibility

The PS will be generated by a logistic regression model using the baseline demographic and disease characteristics in Table 1 as covariates. The final PS will be based on informative variables from the multivariate logistic regression model.

Table 1. Selected Variables for the Estimation of PS

Baseline Characteristics	Value
Race	Black, White, Unknown
BMI (overweight)	Yes (≥ 25), No (< 25), Unknown
Metastatic sites	Bone only, Visceral disease, non-visceral disease
Number of metastatic site(s)	1, 2, 3+
Stage at diagnosis	I, II, III, IV, Unknown
ECOG performance status score	0, 1, 2+, Unknown
Prior neo/adjuvant chemotherapy	Yes, No
Disease-free interval	< 12 months, ≥ 12 months, De Novo, Unknown

It is important to emphasize that using PS methodology to balance the baseline characteristics between the 2 cohorts will be performed independently of tumor response outcome. To fulfil this requirement, data transfer from USON will be divided into 2 steps:

Step 1: Baseline and disease characteristics will be transferred first to perform balancing using PS analysis and make the PS match, calculate IPTW weights, and generate quintile strata. For each different patient population, the PS will be re-run so that the baseline characteristics are balanced between the 2 cohorts for the analysis.

Step 2: Only after the balancing process is completed for each planned analysis, **CCI** [REDACTED] the data containing outcome variables (tumor assessments) will be transferred to Pfizer to perform the analyses for estimating the treatment effect (rwRR).

8.2.2. Primary Analyses of rwRR

The primary endpoint is rwRR, which is defined as the proportion of real-world tumor response of CR or PR based on response assessments captured with chart review during first line therapy.

The primary analysis is to estimate the rwRR between the 2 cohorts (palbociclib plus AI vs AI monotherapy) using the IPTW method to adjust for the potential imbalance of the eight baseline demographic and clinical characteristics (Section 8.2.1) between the 2 treatment cohorts.

The rwRR will be estimated for each treatment cohort and compared for patients in the analysis set adjusted by nIPTW.

- The number and percentage of patients with a best response of CR, PR, SD, PD, and NE will be tabulated.
- A weighted proportion of patients based on nIPTW achieving rwRR (CR or PR) will be summarized along with the corresponding exact 2-sided 95% CI calculated using a method based on Wilson score method.
- Odds ratio for rwRR with the corresponding 2-sided 95% CIs will be calculated based on weighted rwRR using the CMH method.

Analyses using nIPTW method will be performed in the following 2 analysis sets. PS will be re-estimated for each analysis set.

1. Full analysis set. Patients who had no tumor assessments documented on treatment will be considered as non-responders in the assessment of rwRR.
2. Analysis set for patients with at least one tumor assessment.

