HER2	human epidermal growth factor receptor 2
HR	hormone receptor
HR	hazard ratio
ICD	International Classification of Diseases
IHC	International Council for Harmonisation
iKM	iknowMed
ILD	interstitial lung disease
IPTW	inverse probability of treatment weighting
LOT	line of therapy
MBC	metastatic breast cancer
MI	multiple imputation
nIPTW	normalized inverse probability of treatment weighting
NOS	not otherwise specified
PD	progressive disease
PR	partial response
PS	propensity score
PSM	propensity score matching
rwCR	real world complete response
rwPR	real world partial response
rwRR	real world response rate
rwTR	real world tumor response
SAP	statistical analysis plan
SD	Stable disease
std dev	standard deviation
TNM	Tumor, Node, Metastasis
US	United States
USON	United States Oncology Network
USPI	United States Prescribing Information

AMENDMENTS FROM PREVIOUS VERSION(S)

CCI

In the protocol and draft SAP, the number of patients in the final datasets based on structured data was 316 (139 in palbociclib plus AI cohort and 177 in AI monotherapy cohort). After chart review to confirm patient eligibility, the actual number of patients who met inclusion/exclusion criteria is 196 (116 in palbociclib plus AI and 80 in AI monotherapy cohorts). [Figure 1](#) shows the patient attrition.

Since the number of patients in the control cohort (AI monotherapy) is less than that in the treatment cohort (palbociclib plus AI), a significant number of patients in the treatment cohort did not have a match in the control cohort. Using a greedy nearest neighbor matching strategy (with caliper 0.1), 64 patients from each cohort were matched. Even when the caliper was extended to 0.2, only 69 patients were matched from each cohort. Therefore, due to the risk of substantial loss of information, the PSM method is not considered appropriate for the primary analysis.

Based on baseline data, following changes were made to the draft SAP CCI

- 1) Perform the primary analysis using IPTW to adjust for imbalance of potential confounding factors between the 2 cohorts.
- 2) PSM method will be used as a sensitivity analysis.

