8.1.3. Propensity Score (PS)

Because of the lack of randomization in this real world non-interventional study, PS-based analysis will be used to control the potential imbalance in baseline demographic and clinical characteristics between the 2 comparison cohorts in the statistical analyses. [1,2]

The PS is the probability of treatment assignment conditional on observed baseline characteristics. The PS allows one to design and analyze an observational (nonrandomized) study so that it mimics some of the particular characteristics of a randomized controlled trial.

The PS is defined as the probability of receiving the active treatment ($Z=1$ vs $Z=0$), conditional on observed baseline covariates (X): $P_i = Pr(Z_i=1 | X_i)$ for a participant i . It is a balancing score: conditional on the PS, the distribution of measured baseline covariates is expected to be the same between palbociclib plus AI cohort and AI monotherapy cohort.

Similar to randomized clinical trials, PS methods allow one to estimate marginal, rather than conditional measures of treatment effect. The reason for this can be clearly seen for matching, stratification, and weighting: one is comparing average outcomes between samples of cohort A and cohort B subjects who have the same distribution of observed baseline covariates.

Clinically relevant baseline variables associated with treatment assignment and treatment outcome (tumor response) will be selected based on clinical judgement and be used in logistic regression model to estimate PS.

A PS (value from 0 to 1) will be generated using a multivariable binomial logistic regression model with treatment (palbociclib + AI vs AI monotherapy) as dependent variable and selected informative baseline factors as covariates. Once the PS is estimated, it is important to make sure the measured covariates are balanced in order to reduce overt bias. Several methods can be used to assess the balance including:

- **Standardized mean differences of each covariate between treatment groups.** Standardized mean differences could be used to quantify the magnitude of the difference between baseline characteristics of two cohorts. A standardized difference of 0.1 or less will be considered as well balanced between the two cohorts.
- **Graphic of the PS distribution.** The distribution of the PS between the two cohorts should overlap. Nonoverlapping distributions suggest that one or more baseline covariates are strongly predictive of treatment selection.

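### The primary intervals in SAP 8.2.2 name no variance that reflects the unequal weights or the estimated propensity score; modelled control coverage is about 0–3 points below 95%, and the odds-ratio interval can err either way

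*SAP*

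**What the plan says.** The SAP made IPTW the primary method after chart review left 116 palbociclib + AI and 80 AI-alone patients (Amendments from previous version(s); Section 5).

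- **Rates (8.2.2):** "A weighted proportion of patients based on nIPTW achieving rwRR (CR or PR) will be summarized along with the corresponding exact 2-sided 95% CI", computed by a method based on the Wilson score.
- **Odds ratio (8.2.2):** its interval "will be calculated based on weighted rwRR using the CMH method".
- **Weights (8.1.5):** each weight is multiplied by N and divided by the cohort's sum of weights. "After normalization, the total number of patients in the weighted population will stay the same as unweighted population".
- **Propensity score (8.2.2):** the PS is a fitted logistic model, and "PS will be re-estimated for each analysis set".
- **Covariates (8.1.3):** "Clinically relevant baseline variables associated with treatment assignment and treatment outcome (tumor response) will be selected based on clinical judgement".
- **Overlap (Amendments):** "Using a greedy nearest neighbor matching strategy (with caliper 0.1), 64 patients from each cohort were matched". Doubling the caliper raised the count by five, to 69 pairs.

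In the supplied text of both documents I find no robust, sandwich, survey-type or bootstrap variance and no effective sample size. Variance appears in the SAP methods only as a ratio used to check matching (8.1.4).

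**The concern.** The standard Wilson and CMH formulas treat counts as independent, equally weighted patients. Rescaling weights to sum to N restores the head count but not the information. Two things are left out, and they pull in opposite directions. Unequal weights raise the variance, so the formula interval is too narrow. Estimating the PS from covariates that predict response lowers it, so the formula interval can be too wide. Nothing makes the two cancel.

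No hypothesis is tested (SAP 4). The two rates, the odds ratio and their intervals are therefore the study's whole answer, and SAP 1 says that answer is meant to support a label expansion. If the interval method is left open, it could also be chosen after the outcomes are seen, which the two-step data transfer in SAP 8.2.1 is meant to prevent.

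**Working it through.** **Inputs.** N = 116 and 80; 64 pairs at caliper 0.1 and 69 at 0.2 (SAP Amendments). Response rates of 58.6% and 39.1% come from the matched US cohort cited in Protocol 7. They are an assumption here, because that cohort was not limited to pre/perimenopausal women. Covariate level frequencies, PS separation and prognostic strength are also assumed.

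**1. The SAP's own figure.** Summing W\* = W × N / ΣW over a cohort gives N. Run on arbitrary weights for N = 80, it sums to 80.0. The statement that the weighted total equals the unweighted total reproduces: 116 + 80 = 196.

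**2. Effective sample size.** n_eff = (ΣW)² / ΣW², which does not change when weights are rescaled. In simulations matched to about 64 and 69 pairs, n_eff is about 64–70 of 80 in control and about 103–107 of 116 in the treated cohort.

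**3. Effect of unequal weights alone.** Design effect D = N / n_eff; approximate coverage = 2Φ(1.96/√D) − 1.
- Control: D = 80/70 to 80/64 = 1.14 to 1.25; coverage 93.3% to 92.0%.
- Treated: D = 116/107 to 116/103 = 1.08 to 1.13; coverage 94.0% to 93.5%.

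The exposure is therefore larger in control.

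**4. Both effects together.** Simulation with a fitted logistic PS on eight Table 1-type factors, 3,000 replicates per row (Monte Carlo SE about 0.5 points). Median pairs were 64/69, or 63/69 in the moderate row.

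| Covariates' link to response | Control SE: actual vs formula | Control coverage | Treated coverage | log OR SE: actual vs formula | OR coverage |
|---|---|---|---|---|---|
| None | 0.0600 vs 0.0542 | 92.4% | 94.0% | 0.328 vs 0.299 | 92.9% |
| Moderate | 0.0592 vs 0.0541 | 93.4% | 94.6% | 0.311 vs 0.299 | 94.6% |
| Strong | 0.0555 vs 0.0542 | 94.3% | 94.8% | 0.271 vs 0.299 | 96.9% |

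A separate simulation at about the same pair counts gave control coverage of 92.2–93.8% (none or weak) and 93.8–95.4% (moderate or strong), and OR coverage of 92.9–97.0%. At slightly poorer overlap (63/68 pairs) with no prognostic effect, control was 91.6% and the OR 91.8%, so the ranges are approximate at their edges.

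**5. What a reader would see.**
- Control rate 39.1%, Wilson: 29.1–50.1% at n = 80 (half-width 10.5 points). The half-width is 11.1 points at n = 70 and 11.6 at n = 64.
- Odds ratio at n = 116/80: responders/non-responders are 68.0/48.0 and 31.3/48.7. OR = (68.0 × 48.7)/(48.0 × 31.3) = 2.20. SE of log OR = √(1/68.0 + 1/48.0 + 1/31.3 + 1/48.7) = 0.297; CI 1.23–3.94.
- The same at effective sizes of 105/66: SE 0.321; CI 1.18–4.13. Both intervals exclude 1.

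**The case against.** **The text permits a valid implementation.** A method based on Wilson could be run at the effective n, where modelled control coverage is 94.7–97.0%. This stands as far as it goes: a reader might infer that the SAP prescribes n = 116 and 80, but it does not write that out. It does not write the alternative either, and the same defence is weaker for the CMH odds ratio.

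**The covariates are chosen to be prognostic.** Under SAP 8.1.3 the moderate or strong rows are plausible, and there the odds-ratio interval is near nominal or conservative. This also stands. A reader might infer that the intervals are always too narrow; the calculation shows otherwise. The strength of the association is not documented, so the favourable rows cannot simply be assumed.

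**Little depends on it.** There is no test to distort, and the matched and quintile-stratified analyses (8.2.3) use no weights. Fair, but those are sensitivity analyses, and the primary result consists of the intervals in question.

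**The size is modelled.** The actual weights and Appendix 2 are not in the supplied text. A reader might infer a large loss of coverage: control does fall to about 74–89% in simulations with only 46–57 pairs at caliper 0.1. The SAP's 64 pairs do not support that setting. A wider set of 20 scenarios at the SAP's pair counts went as low as 90.5% for control, but the two simulations above did not reproduce that, so I do not rely on it.

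**Conclusion.** The point holds as an under-specified variance with modest consequences. At the overlap the SAP reports, the natural reading gives control coverage about 0–3 points below 95% and treated coverage within about 2 points of it. The odds-ratio interval runs from about 2 points too low with weakly prognostic covariates to about 2 points too high with strongly prognostic ones.

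This rests on assumed covariate frequencies, prognostic strength and response rates, and on the inference that n = 116 and 80 are used. That control is the more affected cohort is also modelled, not read from actual weights. At the rates the protocol cites, no conclusion changes. For the set with at least one assessment the same issue applies, but no pair count is given, so I put no size on it.

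**What to change.** Keep the nIPTW point estimates. In SAP 8.2.2, name one primary variance for both rates and the odds ratio. Either of these is acceptable:

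- **A weighted logistic/GEE (survey-type) sandwich.** It is simpler and usually conservative. Modelled coverage: control 93.8–96.6%, OR about 94.6–98%.
- **A bootstrap within cohort that re-fits the PS and weights in each resample.** Modelled coverage: control 94.2–97.5%, OR 94.5–96.3% (400–600 trials, so Monte Carlo SE about 1 point). Add a rule for resamples with empty covariate levels or separation, since Table 1 implies up to 19 PS terms with 80 controls.

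A sandwich that adds the PS-model equations is valid in principle, but it covered only 90.8–93.4% (control) and 92.0–93.9% (OR) here. It would need a small-sample correction.

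Report the effective sample size per cohort for both analysis sets. The PS was already fitted when the SAP was approved, but the documents do not show whether the outcome transfer was still pending. If it was, fix the method before that transfer; if not, say so in the report.

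**Cost.** SAP wording and a little SAS programming, with no new data. The control half-width goes from about 10.5 to 11.3–12.7 points, and mild overcoverage is possible (up to about 98% for the OR).

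**Editorial only.** A Wilson interval is not *exact*. Where 8.1.5 says to "normalize weights and make the sum of the total of weights within one cohort be 1", the sum should read N, to agree with its formula; the weighted proportion is the same either way.

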8.2.3. Sensitivity Analyses of rwRR

Sensitivity analysis will be performed to examine the robustness of the primary analysis.

Sensitivity analysis 1: PSM

Unlike IPTW method in which all patients were included in the analysis, PSM method generates a paired subset of patients based on each patient's PS (Section 8.1.4). In this analysis, rwRR will be estimated in the subset of patients who are 1:1 matched in the 2 cohorts.

- Similar to the primary analysis: The proportion of patients with real-world tumor response (CR or PR) will be summarized along with the corresponding exact 2-sided 95% CI calculated using a method based on Wilson score method.
- Odds ratio for rwRR will be calculated with the corresponding 2-sided 95% CI.

Sensitivity analysis 2: Stratification by PS.

This analysis will divide patients into 5 equal-sized groups using quintiles of the estimated PS. The treatment effect of rwRR (odds ratio) will be estimated using the CMH method stratified by PS quintiles.

Sensitivity analysis 3: Missing value imputation for selected baseline covariates.

This sensitivity analysis is to evaluate the impact of missing values of the eight selected baseline covariates on PS estimation and further on the estimation of the primary endpoint (rwRR). Multiple imputation or other data imputation methods may be explored when appropriate.

8.2.4. Other Analyses

Descriptive analyses:

- For categorical variables (eg, region, race, and stage at initial diagnosis), data will include the frequency (number of cases) and percentage of total patients observed in each category;
- For continuous variables (eg, age and time from initial breast cancer diagnosis to metastatic diagnosis), variables will be presented as the mean, standard deviation, median, 25th and 75th percentiles and ranges (minimum and maximum) in some cases.

The calculation of percentages will always include the missing category in the case of missing values. Continuous variables may be categorized into intervals, with the distribution of patients (N, %) provided.

Menopausal status	iKM structured data + chart review	Baseline	Menopausal status will be first categorized as explicitly documented by physician as: Pre-menopausal Peri-menopausal Among patients lacking a physician-documented menopausal status record, pre-menopausal status will be assigned to those whose sex assigned at birth is female , who are aged less than 60 years and meet either of the following criteria: 
 • No documented history of a prior bilateral oophorectomy • and received an LHRH analog AND/OR 
 • Not amenorrheic
Healthcare setting and provider characteristics			
Practice location	iKM structured data (derived)	Baseline	The US census region of the USON clinic where the patient received care at the index visit: Midwest: Illinois, Indiana, Michigan, Ohio, Wisconsin, Iowa, Kansas, Minnesota, Missouri, Nebraska, North Dakota and South Dakota Northeast: Connecticut, Maine, Massachusetts, New Hampshire, Rhode Island, Vermont, Pennsylvania, New Jersey and New York South: Delaware, Florida, Georgia, Maryland, North Carolina, South Carolina, Virginia, Washington D.C., West Virginia, Alabama, Kentucky, Mississippi, Tennessee, Arkansas, Louisiana, Oklahoma and Texas West: Arizona, Colorado, Idaho, Montana, Nevada, New Mexico, Utah, Wyoming, California, Oregon and Washington State Missing clinic values will be captured in a “no information” category. Some of the regions may need to be collapsed if there are small sample sizes (eg, South versus non-South). This determination will be confirmed after reviewing sample sizes and the added value to the study with McKesson’s Privacy and Compliance team.

Table 2. Study A5481159 Key Variables

Variable	Source(s)	Period of Measurement	Operational Definition
			CCl [REDACTED]
	[REDACTED]	[REDACTED]	[REDACTED]
Practice size	iKM structured data (derived)	01 Jan 2018 – 31 Dec 2018	The number of patients seen at the USON clinic where the patient receive care for his/her index visit in the year 2018: <50 patients/ year 50-99 patients/year 100-149 patients/year ≥150 patients/year
Physician BC patient volume	iKM structured data (derived)	01 Jan 2018 – 31 Dec 2018	The number of BC patients seen by the physician who provided care for the patient's index visit in the year 2018: <10 patients/ year 11-49 patients/year >50 patients/year
Disease characteristics			
Time since initial BC diagnosis	iKM structured data + chart review (derived)	Medical history prior to index	The duration of time, in weeks, between the date of BC diagnosis and presentation of metastatic disease. To assess BC diagnoses that occurred prior to index, patients' available medical history in iKM will searched. The completeness of this history will vary based on the length of disease and the time within the USON. Records may also be incomplete for patients with an initial BC diagnosis that occurred outside of the USON. Diagnosis of BC will be determined through a review of iKM's discrete diagnosis and histology fields, which are populated during the routine course of care (International Classification of Diseases [ICD] codes will not be used). If no initial diagnosis date is documented, the first recorded diagnosis date in iKM will be used. This date will be used in calculations, not reported separately.
Time since MBC diagnosis	iKM structured data + chart review (derived)	Medical history prior to index	The duration of time, in weeks, between the index date and presentation of metastatic disease. Date of first recorded diagnosis of metastatic disease within the EHR. Patients will be qualified initially based on the date identified in the structured data; this will be confirmed during chart review among patients selected for chart review. Ultimately, the primary source will be the chart if available. Patients without recorded evidence of metastatic disease will be excluded from the study. Structured data will confirm the patient as metastatic and as available, indicate the earliest associated date of any of these criteria: 1) Stage IV disease

Table 2. Study A5481159 Key Variables

Variable	Source(s)	Period of Measurement	Operational Definition
			
2) Tumor, Node, Metastasis (TNM) stage with M value of 1 3) Record of location of metastatic disease 4) Current or prior disease status containing reference to metastatic disease

Distant metastatic site(s)	iKM structured data + chart review	Medical history prior to index	
Baseline metastatic location(s) will be captured as documented in patients' charts. Note, patients that lack documented metastatic sites can indicate that metastases were not documented in the chart, not necessarily that patients did not have metastases.

Visceral/non-visceral status Bone only	iKM structured data + chart review (derived)	Medical history prior to index	
Categorized as outlined below (not mutually exclusive) except for bone only, in which patients will have bone as their only metastatic site(s) identified:
 
Visceral: Liver Lung Pleura
 
Other (not exhaustive): Adrenal gland Ascites Axilla Bilateral intraocular Brain Breast Bronchus Cervical nodes Cervix Chest wall Duodenum, retroperitoneum & mesentery Esophagus Eye Fallopian tube Gallbladder Gastrointestinal tract/stomach Genital organ Intestinal tract Kidney Large intestine Leptomeningeal Leptomeninges Lymph nodes – distant

Table 2. Study A5481159 Key Variables

Variable	Source(s)	Period of Measurement	Operational Definition
			
Lymph nodes – NOS Lymph nodes – regional Mediastinum Muscle Omentum Other parts of nervous system Other respiratory organ Other urinary organ Ovary Pancreas Pericardial effusion Pericardium Peritoneum Pleural effusion Rectum Retroperitoneum Skin Small intestine Soft tissue Spinal cord Spleen Bone (not exhaustive): Bone Bone marrow Pelvis Ribs Skull Spine 

Count of metastatic site(s)	iKM structured data + chart review (derived)	Baseline	
The total count of metastatic site(s) at index: No information 1 2 3 4+
 
Note, “no information” can indicate that metastases were not documented in the chart, not necessarily that patients did not have metastases.

Table 2. Study A5481159 Key Variables

Variable	Source(s)	Period of Measurement	Operational Definition																					
Stage at diagnosis	iKM structured data	Medical history prior to index	
Categorized as:
 
 Stage 0 Stage IA Stage IB Stage IIA Stage IIB Stage IIIA Stage IIIB Stage IIIC Stage IV No information 																					
Eastern Cooperative Oncology Group (ECOG) performance status	iKM structured data + chart review	Baseline	
The ECOG performance status score is a rating of a patient's disease status, daily living activities and quality of life, with low scores indicating greater functioning than high scores:
 
 0 1 0/1 2 2+ 3+ No information 
Karnofsky performance status is a similar measure and will be converted to ECOG using the methodology outlined below.
 
  
 Karnofsky Performance Status	ECOG Performance Status	ECOG Performance Status Description	
   
 100	0	Fully active	
 
 80, 90	1	Restricted in physically strenuous activity	
 
 60, 70	2	Ambulatory and capable of self-care but unable to work	
 
 40, 50	3	Capable only of limited self-care	
 
 10, 20, 30	4	Completely disabled	
 
 0	5	Dead	
  
	Karnofsky Performance Status	ECOG Performance Status	ECOG Performance Status Description	100	0	Fully active	80, 90	1	Restricted in physically strenuous activity	60, 70	2	Ambulatory and capable of self-care but unable to work	40, 50	3	Capable only of limited self-care	10, 20, 30	4	Completely disabled	0	5	Dead
Karnofsky Performance Status	ECOG Performance Status	ECOG Performance Status Description																						
100	0	Fully active																						
80, 90	1	Restricted in physically strenuous activity																						
60, 70	2	Ambulatory and capable of self-care but unable to work																						
40, 50	3	Capable only of limited self-care																						
10, 20, 30	4	Completely disabled																						
0	5	Dead																						

Table 2. Study A5481159 Key Variables

Variable	Source(s)	Period of Measurement	Operational Definition
CCI (Charlson Co-morbidity Index) score	Chart review	Prior medical history	
Calculated based on the presence of 17 Charlson comorbidities at MBC diagnosis.
 
Comorbidities and associated obfuscated dates documented prior to or on the index date will be captured and summarized as:
 
Myocardial infarction, congestive heart failure, peripheral vascular disease, cerebrovascular disease, hemiplegia or paraplegia, chronic pulmonary disease, peptic ulcer disease, diabetes with chronic complications, diabetes without chronic complications, renal disease, rheumatologic disease, dementia, mild liver disease, moderate or severe liver disease, any malignancy including leukemia and lymphoma, metastatic solid tumor, HIV/AIDS.
 
In addition, history of interstitial lung disease (ILD) and pneumonitis will be noted but not included in the CCI score.
 
Two approaches will be used to capture comorbidities documented in patients' medical records. First, comorbidities explicitly documented by providers will be captured and reported. Separately, patients with suspected comorbidities based on receipt of medications associated with those conditions will be identified.
 
To identify suspected comorbidities, an extract of all concomitant meds documented pre-index for the study population cohorts will be generated with patients' entire treatment history documented in the structured data. The study team, including clinical experts and the Physician Investigator, will review the frequency distributions of the medications and map these to chronic conditions.
 
For analysis purposes, comorbidities explicitly documented by providers versus those imputed by medication use will be differentiated.

Disease histology	iKM structured data	Prior medical history	Categorized as: Ductal Lobular Mixed Metaplastic Tubular Mucinous Other No information
BRCA 1/2 status	iKM structured data + chart review	Prior medical history	Categorized as: Positive Negative No information
ESR1 status	iKM structured data + chart review	Prior medical history	Categorized as: Positive Negative

Table 2. Study A5481159 Key Variables

Variable	Source(s)	Period of Measurement	Operational Definition
			No information
NGS status	iKM structured data + chart review	Prior medical history	Categorized as: Positive Negative No information
Treatment characteristics			
Pre-index treatment(s)	iKM structured data + chart review	Medical history prior to index	Patients' treatments received prior to index, along with obfuscated dates. This includes prior adjuvant hormonal treatment or prior neo-adjuvant/adjuvant chemotherapy.
Adjuvant treatment end dates	iKM structured data + chart review	Medical history prior to index	Obfuscated date of adjuvant treatment discontinuation.
Endocrine sensitivity	iKM structured data + chart review (derived)	Medical history prior to index	Relapse more than 12 months after completing adjuvant endocrine therapy
Disease-free interval	iKM structured data + chart review (derived)	Medical history prior to index	Obfuscated dates between discontinuation of adjuvant therapy and the start of treatment for unresectable and/or metastatic disease.
Radiotherapy	iKM structured data + chart review	Medical history prior to index and study observation period	All radiotherapy, along with obfuscated dates, received prior to or during the study observation period will be captured. During analysis, 2 variables will be constructed: “Concomitant radiotherapy” will be defined as radiotherapies given during 1L treatment “Prior radiotherapy” will be defined as all radiotherapies prior to index date
Index treatment regimen	iKM structured data + chart review	Study observation period	Patients' index treatment will be categorized based on the cohort descriptions in Protocol Section 9.1: Palbociclib combination therapy with an AI (letrozole, exemestane or anastrozole) or AI monotherapy
Date of treatment initiation during the patient identification period (ie, index date)	iKM structured data + chart review	Study observation period	The obfuscated date of initiation with a palbociclib-based combination regimen or AI monotherapy (letrozole, exemestane or anastrozole) during the study identification period. If a regimen consists of more than one drug with drugs given on different dates, the date of the first administration of any drug will be used.
Index treatment end date(s)	iKM structured data + chart review	Study observation period	Obfuscated date of final treatment for each drug or regimen. If a regimen consists of more than one drug with drugs ending on different dates, the date of the last administration of any drug will be used. It is possible that the patient's treatment stop date is not documented if the patient dies, is lost-to follow-up or is still on-therapy. The final treatment date, death date or end of study date will be used, whichever is earliest.
Index line of therapy (LOT)	iKM structured data	Study observation period	LOT will be operationally defined as a course of care that continues until disease progression or unacceptable toxicity. As such, advancement in LOT will be assigned if there is a change in regimen due to documented progression. The only exception is switching between AIs (exemestane, letrozole, anastrozole) will not constitute a change in LOT, unless the change in AI is due to documented progression.

Table 2. Study A5481159 Key Variables

Variable	Source(s)	Period of Measurement	Operational Definition
Number of cycles (index treatment)	iKM structured data	Study observation period	The number of provider-documented therapy cycles received for the index treatment.
Index treatment schedule (cycle length and frequency)	iKM structured data + chart review	Study observation period	The planned frequency and cycle length of the index treatment.
Index treatment schedule changes	iKM structured data + chart review	Study observation period	Each index treatment (either AI monotherapy or palbociclib combination therapy) schedule change will be captured and reported, along with the obfuscated date.
Index palbociclib treatment starting dose	iKM structured data + chart review	Study observation period	
The actual index treatment starting palbociclib dosage received.
 
Categories to be presented:
 
 75 mg 100 mg 125 mg Other No information
Palbociclib combination regimen	iKM structured data + chart review	Study observation period	
Classification of patients into the following treatment groups:
 
 Palbociclib-letrozole Palbociclib-anastrozole Palbociclib-exemestane
Reason for palbociclib dose changes	Chart review	Study observation period	
Data for palbociclib dose change reason will exclusively come from chart review. Reviewers will be asked to select reason(s) as explicitly documented in patients' charts.
 
If available, reason patients discontinued treatment will be abstracted:
 
 Lack of response Patient preference Toxicity Other No information 
Reviewers will specify other reasons; these will be reported if any represent >5% of patients.

Reason for treatment discontinuation (all treatment lines)	Chart review	Study observation period	
Data for discontinuation reason will exclusively come from chart review. Reviewers will be asked to select reason(s) as explicitly documented in patients' charts.
 
If available, reason patients discontinued treatment will be abstracted:
 
 Provider-documented disease progression Toxicity Decline in performance status Financial/insurance

Table 2. Study A5481159 Key Variables

Variable	Source(s)	Period of Measurement	Operational Definition
			
Completed planned treatment Death Hospice Patient preference Physician preference Other No information Reviewers will specify other reasons.

Reason for treatment initiation (all treatment lines)	Chart review	Study observation period	
Data for treatment initiation reason will exclusively come from chart review. Reviewers will be asked to select reason(s) as explicitly documented in patients' charts.
 
If available, reason for treatment initiation will be abstracted:
 
 Initial diagnosis Initial diagnosis with unresectable disease Initial diagnosis with metastatic disease Progressive disease Other reasons; non-progression Toxicity on prior therapy Reason not specified 
Reviewers will specify other reasons.

Post-index treatment(s)	iKM structured data + chart review	Study observation period	Patients' treatments received after index, along with obfuscated dates.
Provider-documented tumor assessments			
Provider-documented tumor assessment	Chart review	Study observation period	
In prospective clinical trials, response is generally assessed according to Response Evaluation Criteria In Solid Tumors (RECIST) criteria. However, the parameters underlying these criteria are less reliably available in retrospective, observational studies. Instead, for this study, provider documented assessments of tumor response will be used. No attempts will be made to mimic the RECIST guidelines.
 
Response assessments documented for the index treatment (depending on cohort). It is possible that patients have multiple response assessments in their charts during this period.
 
All documented responses to the index treatment (AI monotherapy or palbociclib combination therapy) described within progress notes (along with the associated, obfuscated progress note date) will be captured. For each tumor assessment, it will be documented if a scan report was documented as the basis of the assessment.
 
Tumor assessments will be classified as:
 
Complete response: Documented as "a complete response" to therapy; indication patient is in "remission"; "all lesions" have disappeared or "no evidence of disease").

Table 2. Study A5481159 Key Variables

Variable	Source(s)	Period of Measurement	Operational Definition
			
Partial response: Documented as partial reduction in size of visible disease in some or all areas without any areas of increase in visible disease (decrease in disease volume even though disease is still present).
 
Stable disease: Documented as disease is stable (not progressed or not improved; e.g. Stable appearance of lobe nodules and Mixed response: Combination of improved and worsened disease).
 
Progressive disease: Documented as disease has “progressed”; or worsening of disease.
 
Not evaluated: No documentation of status of disease.

Clinical outcomes			
Last USON visit date	Chart review	Study observation period	Patients' last visit date will be captured through chart review as a verified physical encounter with the practice as evidenced by treatment administration, measurement of vital signs, laboratory specimen collection or other office procedures. For patients with a death date, this last visit date should occur prior to the death date.
